6. TIMETABLE	
APPENDICES	24
REFERENCES	24

1. Introduction and background

There is growing evidence of the promise and potential of gender-transformative programs – which actively engage participants in reflecting on and challenging inequitable gender norms and power dynamics – with fathers to promote the health and well-being of their partners, children, and men themselves. The Bandebereho intervention works with men and couples to promote men's engagement in maternal and newborn health, equitable caregiving, healthier couple relations and the prevention of violence against women and children. The intervention, inspired by Promundo's Program P, was adapted to the Rwandan context by the Rwanda Men's Resource Center and Promundo, and approved by the Ministry of Health.

From 2013-2015, RWAMREC piloted Bandebereho with more than 3,500 parents in four districts (Karongi, Musanze, Nyaruguru, Rwamagana). Rwanda represented a strategic place to rigorously evaluate a gender-transformative male engagement approach. The country has made significant strides in reproductive and maternal health and the promotion of gender equality, and its policies acknowledge that progress on sexual, reproductive, and maternal health and violence prevention require interventions with men and couples to promote equitable gender relations, women's decision-making power, and reduced IPV.^{i,ii}

1.1. Description of the intervention being evaluated

The Bandebereho couples' intervention being assessed was concluded in 2015. The intervention engaged men and their partners in participatory, small group sessions of critical reflection and dialogue. The intervention used a structured curriculum which was approved by the Rwanda Ministry of Health/Rwanda Biomedical Center. Men participating in the Bandebereho intervention were invited to 15 sessions (maximum 45 hours) and their partners to 8 (maximum 24 hours). Sessions addressed: gender and power; fatherhood; couple communication and decision-making; intimate partner violence; caregiving; child development; and male engagement in reproductive and maternal health.

The intervention creates a structured space for men and women to:

- question and critically reflect on gender norms and how these shape their lives;
- rehearse equitable and non-violent attitudes and behaviors in a comfortable space with supportive peers; and
- internalize these new gender attitudes and behaviors and apply them in their own lives and relationships.

Results from the evaluation showed that becoming aware of inequalities, reflecting on the costs of rigid norms, and learning and practicing new skills (e.g., couple communication and joint decision-making) in a safe, non-judgmental peer environment, lead to changes across a range of health and relationship behaviors.

Community volunteers (local fathers) met with the same group of 12 men/couples on a weekly basis. The volunteers received a two-week training, material support, and refresher trainings from RWAMREC. Local nurses and police officers co-facilitated the sessions on pregnancy, family planning, and local laws, respectively. Sessions were conducted in local schools and administrative offices. RWAMREC staff monitored implementation of the group sessions and mentored the facilitators. Three intervention cycles, each with 570–576 couples, were implemented between March 2014 and July 2015. The Bandebereho RCT assessed the third cycle. The control group received no group intervention, though it did have access to community activities and campaigns related to the broader MenCare+ project through which the Bandebereho couples' groups were implemented. The intervention has been documented in greater detail in Doyle et al (2018).

1.2 Previous evaluation findings

A randomized controlled trial (RCT) of the Bandebereho intervention was previously conducted with 1,199 couples (575 treatment; 624 control) and demonstrated significant impacts on a range of gender and health-related outcomes. As reported in PLOS One^{iii} , at 21-months after the baseline (16 months post-intervention), compared to a control group, participating families reported: less past-year physical (OR 0.37, p<0.001) and sexual intimate partner violence (IPV) (OR 0.34, p<0.001), and less physical punishment of children (women: OR 0.56, p = 0.001; men: OR 0.66, p = 0.005). Women in the intervention reported greater antenatal care (ANC) attendance (IRR 1.09, p<0.001) and male accompaniment to ANC (IRR 1.50, p<0.001), as well as modern contraceptive use (OR 1.53, p = 0.004), compared to women in the control group. Additionally, women in the intervention group reported higher levels of men's participation in childcare and household tasks (women: beta 0.39, p<0.001; men: beta 0.33, p<0.001) and less dominance of men in a series of household decisions. Forthcoming analyses also indicate that compared to the control group, the intervention group reported: lower rates of maternal depression, lower rates of men's alcohol consumption, and greater time spent by parents in stimulating interaction with their children.

The results of the Bandebereho RCT have contributed to critical evidence gaps on the impact of male engagement approaches. While several trials from the Global South had previously shown positive impacts on outcomes related to intimate partner violence (IPV),^{iv,v,vi,vii,viii} family planning,^{ix,x} and maternal health,^{xi,xii,xiii} rigorous evidence of effectiveness of male engagement approaches has remained limited.^{xiv,xv,xvi} In addition, few studies have evaluated interventions addressing multiple outcomes and even fewer have examined impact on household gender and power dynamics^{xvii,xviii} in the way that the Bandebereho RCT has done. While the Bandebereho RCT collected data over a longer timeframe than many studies (at 16 months post-intervention), it does not provide an understanding of the longer-term impacts of the intervention.

1.3 Proposed research

We seek to conduct a six-year follow-up of the Bandebereho RCT to understand the longer-term impact of the intervention on participating couples. In addition, we wish to expand our study to incorporated direct observation of child development outcomes, to better assess the intervention's impact on children of participating couples. We know that young children's growth and development is particularly impacted by their relationships – or lack thereof – with caring, engaged, and responsive parents and caregivers. Children's highest potential is supported when they are raised in a home that is free from violence – against children and against their mothers – by caregivers who foster a sense of being loved, protected, and cared for, and who respect each other and share equitably the childrearing.

The results from the Bandebereho RCT – which indicated parents' reduced use of harsh or physical discipline against their children – suggest enormous promise for the intervention to have measurable impacts on the development and well-being of children through the transformation of the couple relationship and home environment. Violence can lead to severe consequences for children. In addition to the risk of immediate injury, studies have shown that exposure to extreme trauma and "toxic stress" during early developmental stages – including both experiencing violence and witnessing it – can severely damage the organization of the brain by disrupting proper development. Indeed, violence affects children's mental health, their learning and performance in school, and creates difficulties in developing empathy, controlling aggression, and interacting with others, and damages parent-child relationships.^{xix,xx}

We have a unique opportunity to assess child outcomes as well as the sustainability of changes in the couple dynamics six years after the intervention began: few interventions in either the early child development field or the violence against women field have been able to track results over such a time frame. As attention to both early child development (ECD) and violence prevention increases, a longer-term study can provide much needed evidence. The six-year follow-up will add a unique and valuable contribution to the existing evidence on gender-transformative male engagement interventions, by: a) providing data on the longer-term impact of the intervention (including whether previous outcomes have been sustained), and b) providing data on if the intervention shows measurable impacts on children's cognitive and social and emotional development outcomes. In addition, Promundo and RWAMREC are currently working with the Rwanda Biomedical Center to scale-up the Bandebereho intervention via the health sector in Musanze district, by training more than 400 community health workers to implement the program as part of their routine health promotion work. The findings will strengthen and inform the ongoing scaling of the intervention.

2. Study objectives

This study is a six-year follow-up of the Bandebereho RCT. This round of data collection will be (up to) the fourth contact with study participants. Three previous rounds of data collection were

conducted as part of the Bandebereho RCT: a baseline in 2015, a 9-month follow up in 2015, and a 21-month follow up in 2016. In 2020, a phone survey focused on COVID-19 was conducted with a subsample of 500 men and 498 women enrolled in the study.

The aim of this study is to assess the longer-term, six-year impact of the gender-transformative Bandebereho intervention on participating couples and their children, when compared to the control group. The specific objectives of the study are:

- a) To understand the longer-term impacts of the Bandebereho intervention on men's and women's behaviors and experiences, including caregiving, couple dynamics, parenting, reproductive health, and intimate partner violence.
- b) To understand the impact of the Bandebereho intervention on young children's cognitive and social-emotional development.

A table of key indicators is included in Table 4.1: Primary Outcomes and Indicators, in Section 4.1.

3. Study Methodology

3.1. Study description

This study is designed as a six-year follow-up of the Bandebereho randomized controlled trial (RCT) to evaluate the longer-term impacts of the Bandebereho gender-transformative, couples' group intervention on participating men, their partners, and a sub-sample of children. The study design and sampling of adult participants are thus based on the original study design and sample, approved by NISR (9 February 2015, 0082/2015/NISR), the Rwanda National Health Research Committee (25 August 2014, NHRC/2014/PROT/0193), and the Rwanda National Ethics Committee (24 October 2014, 346/RNEC/2014).

[figure not shown]
3.2. Study design

The study is designed as a six-year follow up of a randomized control trial with two arms: intervention and control. Couples were recruited into the intervention via the male partner in early 2015 and were later randomized to either the intervention or a control group. Due to the nature and structure of the intervention, randomization was done at the individual level. Randomization for the Bandebereho study took place in 2015, following the baseline survey (using the individual as the unit of randomization). The randomization was done by Laterite, an independent data collection firm, using a random number generator in Stata. Of the 1,199 men enrolled in the study, 575 men and their partners were randomized to the intervention (Bandebereho) group and 624 men and their partners were randomized to a control group, which received no intervention. Bandebereho community facilitators notified men of their assignment. All recruited men remained eligible for randomization to the intervention regardless of participation in baseline data collection.

The flow diagram of the Bandebereho RCT is included as Appendix 2.

Data were previously collected at three time points: baseline (February/March 2015); 9-month follow-up (November/December 2015); and 21-month follow-up (November/December 2016). Data were also collected from a subsample of respondents by phone, in August 2020, to better understand the impact of the Covid-19 virus on their lives. The proposed six-year follow-up will collect data in April and May 2021, approximately 72 months post-baseline. The study will seek to conduct in-person surveys with all couples enrolled in the original study (who are alive and traceable) and to conduct child assessments with a sub-sample of 800 children from 800 families.

Figure 1. Bandebereho RCT timeline

3.3. Study site

The study site includes communities in 16 sectors within the 4 districts (Karongi, Musanze, Nyaruguru, and Rwamagana) where: a) the Bandebereho project was implemented from 2013-15, in collaboration with the Ministry of Health and local authorities; and b) where the previous rounds of data collection of the Bandebereho RCT took place. The sectors (4 per district) include:

- Karongi district (Western Province):
- Musanze district (Northern Province):
- Nyaruguru district (Southern Province):
- Rwamagana district (Eastern Province):

Data will also be collected from RCT participants who have relocated outside of these locations but are willing to travel to a data collection site to be surveyed.

3.4 Sampling

3.4.1. Sampling frame

The sampling frame for this study includes all participants from among the 1,199 couples (576 treatment; 624 control) who enrolled in the original RCT study in 2015, who are living, traceable, and remain eligible for the study. We will also conduct child assessments with a randomly selected subsample of 800 of their children born around or shortly after the intervention, aged between 4 and 7 years (400 treatment; 400 control).

3.4.2. Inclusion and exclusion criteria

This six-year follow-up seeks to survey all men who have participated in a previous round of data collection for the Bandebereho RCT and their current female partners. The original inclusion and exclusion criteria are described in Appendix 1. The inclusion and exclusion criteria for this round of data collection are outlined in Table 3.4.2. Note that all men who were recruited into the original study were older than 18 years; men may have new partners in this round of data collection, therefore their female partners must be at least 18 years old to be eligible. While women's inclusion is dependent on a current relationship with a man eligible for inclusion in the study, it does not depend on whether the male partner is surveyed at the six-year follow-up. The current study also seeks to measure child development outcomes on a subsample of children from enrolled couples, whose inclusion criteria are also described in Table 3.4.2.

Study population	Inclusion criteria	Exclusion criteria
Men	 a) Enrolled in the original Bandebereho RCT b) Participated in at least one (of three rounds) of previous RCT data collection conducted between 2015-16 c) Currently partnered (married or cohabiting) with a female partner d) Currently resides in the four districts included in the original study (Karongi, Musanze, Nyaruguru, Rwamagana), or is able to travel to one of these data collection sites 	 a) Resides outside of the sites selected for this study and specified follow-up locations, and is unable to travel to one of the data collection sites b) Unable to provide informed consent

Women	 a) Currently partnered (married or cohabiting) with a man eligible for inclusion in the current study b) Currently resides in the four districts included in the original study (Karongi, Musanze, Nyaruguru, Rwamagana), or is able to travel to one of these data collection sites c) At least 18 years of age or older 	 a) If partner enrolled in the RCT is deceased b) Resides outside of the sites selected for this study and specified follow-up locations, and is unable to travel to one of the data collection sites c) Unable to provide informed consent
Children	 a) Aged between 4 and 7 years; b) Biological child (of the male partner) living in the household of a man enrolled in the Bandebereho RCT; c) Whose parent has consented to the child's participation in the study d) Child provides assent to participate 	 a) If the child lives outside of the household (e.g. with other relatives, at an institution) b) If another child in the same family has been selected for assessment

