3.4.4 Sample selection

The primary sampling unit, and unit of analysis, is the individual respondent within the household. All men enrolled in the original Bandebereho RCT who are known to still be alive at the 21-month

follow-up (n=1,193) will be assessed for eligibility in the current study and included in the sample, as well as their current female partners.

For the six-year follow-up, we will be randomly selecting 800 households with children ages 4-7 for observational assessments of a selected child. The children will be selected randomly from a list of families with eligible children, stratified by intervention and control group status, as well as by district. Only one child per family would be eligible for assessment. If the family has more than one child ages 4-7, the child closest to age 6 would be selected. If more than one child fits that criterion (e.g. one child age 5 and another child age 7), the youngest child is selected. If the family has twins ages 4-7, one child is randomly selected.

Sampling will be done by Laterite, an external data collection firm.

4. Research instruments, outcome measurement and analysis plans

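### Men's criterion (b) can exclude a randomised man who missed baseline because he also missed two post-randomisation survey rounds; the number is unknown and probably small, but the exclusion is avoidable.

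*Protocol*

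**What the plan says.** Protocol section 3.4.2 states the rule twice. The opening sentence reads "This six-year follow-up seeks to survey all men who have participated in a previous round of data collection for the Bandebereho RCT", and Table 3.4.2 repeats it as men's criterion (b): "Participated in at least one (of three rounds) of previous RCT data collection conducted between 2015-16".

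Section 3.2 dates the three rounds: "baseline (February/March 2015); 9-month follow-up (November/December 2015); and 21-month follow-up (November/December 2016". It also says "Randomization for the Bandebereho study took place in 2015, following the baseline survey", and that "All recruited men remained eligible for randomization to the intervention regardless of participation in baseline data collection". Men were told their assignment by the community facilitators.

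Section 3.2 describes the target of the six-year round without any condition on earlier response: "The study will seek to conduct in-person surveys with all couples enrolled in the original study (who are alive and traceable". Section 3.4.4 says that the men known to be alive at the 21-month "follow-up (n=1,193) will be assessed for eligibility in the current study and included in the sample".

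Under women's criterion (a) in Table 3.4.2, a woman must be the current partner of a man who is himself eligible for this round.

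**The concern.** The value of a six-year follow-up of a randomised trial is that the arms are still compared as they were formed in 2015. An eligibility rule that depends on something observed after allocation can weaken that.

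For a man with no baseline interview, criterion (b) is such a rule. Under section 1.1, intervention men belonged to groups that met weekly, while controls received no group intervention. Whether a man later answered at least one survey could therefore depend on his arm. This differs from ordinary non-response at six years, because a man who is found and willing would be turned away.

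The loss extends to his partner. Table 4.1 takes past-year intimate partner violence from women only, and section 5.8.3 confirms that men are not asked about perpetration. So the man's silence in 2015-16 would remove a woman's report of a primary outcome. Section 3.4.2 makes her inclusion independent of whether he is surveyed at six years, but not of whether he was surveyed before.

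**Working it through.** **Who is affected.** The dates in section 3.2 put one round before randomisation and two after it. The groups assessed in the trial had finished by July 2015 (section 1.1), so men knew their arm before the 9-month round in November/December 2015.

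- Surveyed at baseline: criterion (b) is met before randomisation, whatever happened later.
- Missed baseline, answered at 9 or 21 months: met, but only through a post-randomisation response.
- Missed all three: not met; the man and his partner are excluded.

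Only men who missed baseline can be affected.

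**How many.** The protocol text gives no count by round or arm, so the number can only be bounded.

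- Inputs: 1,199 men randomised, 575 + 624 (section 3.2); 94% of men surveyed at 21 months (section 3.4.3); 1,193 known alive at that round (section 3.4.4).
- A man who missed every round missed the 21-month round, so the ceiling is 1,199 × (1 − 0.94) = 71.9, about 72 men (6.0%).
- Rounding of the 94% (93.5% to 94.5%) gives 77.9 to 65.9.
- If the 1,199 − 1,193 = 6 men not known to be alive are among those 72, the ceiling falls to about 66.
- The floor is 0.

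To see where in that range the number may lie, assume that 1% to 10% missed baseline and 3% to 10% missed the 9-month round. Neither rate is in the protocol.

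- Missing rounds independently: 1,199 × 0.01 × 0.03 × 0.06 = 0.02 men, up to 1,199 × 0.10 × 0.10 × 0.06 = 0.7 men.
- Fully overlapping non-response (number = 1,199 × the smallest of the three rates): 1,199 × 0.01 = 12 men, up to 1,199 × 0.06 = 72 men.

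**Effect on the estimate.** Let e0 and e1 be the shares excluded in control and intervention, and D the outcome difference between excluded and included men, taken as equal in both arms. The bias in the arm difference is (e0 − e1) × D. All values below are assumptions.

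| e0 | e1 | D (points) | Bias (points) |
|---|---|---|---|
| 1% | 0% | 20 | 0.01 × 20 = 0.2 |
| 6% | 3% | 20 | 0.03 × 20 = 0.6 |
| 6% | 0% | 30 | 0.06 × 30 = 1.8 |

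The last row is a severe case, not a strict limit. If all 72 men were controls, the share would be 72/624 = 11.5% and the bias 0.115 × 30 = 3.5 points, but nothing in the protocol suggests so one-sided a loss. These figures also assume that the excluded men would otherwise have been surveyed at six years. If many would not, the part due to criterion (b) is smaller.

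**Effect on precision.** Losing 72 of 1,199 men multiplies the standard error by √(1,199/1,127) = 1.031, about 3%.

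**The case against.** The strongest reply is that the rule may exclude nobody. Section 3.2 says only that baseline participation was not a condition of randomisation; it does not say that anyone randomised was never surveyed. The flow diagram in Appendix 2, which is not available here, may settle the count. This stands: a reader might infer that randomised men are in fact being dropped, and the text supports only that they can be.

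Four further readings go too far.

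- *That earlier response is a post-randomisation criterion for everyone.* It is not; anyone interviewed at baseline met it before allocation.
- *That section 3.4.4 flatly contradicts the table.* That section has men assessed for eligibility before inclusion, and section 3.4.1 limits the frame to people who remain eligible. The clearer mismatch is with the stated aim in section 3.2.
- *That controls are the ones lost.* Weekly contact makes a difference between arms plausible, but no response by arm is given, so the direction is unknown.
- *That removing (b) restores the population as randomised.* Criteria (c), current partnership, and (d), residence or ability to travel, would remain and are also assessed after randomisation.

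It can also be said that earlier rounds have a practical use. Section 5.1 traces men by the phone number from their latest round, and section 5.9 links data across rounds. But section 5.1 falls back on former facilitators and local authorities, and section 5.2 plans home visits for men without contact details. Linkage does not require an earlier interview either: consent and outcomes are collected afresh, and the arm comparisons in section 4.2 do not call for an earlier measurement.

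**Conclusion.** The point holds in a limited form. Criterion (b) lets post-randomisation response decide the eligibility of men who missed baseline, and of their partners, and this departs from the section 3.2 aim of surveying every enrolled couple that is alive and traceable. The protocol gives no reason for it.

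The number affected is between 0 and about 72 of 1,199 men. It is probably small, since reaching the ceiling requires every 21-month non-respondent to have missed the other two rounds as well. Bias is likely a fraction of a percentage point, and 1.8 points in a severe assumed case. The ceiling rests on the stated 94%; every bias figure rests on assumed exclusion rates and outcome differences. The case for change is that the exclusion is avoidable at almost no cost, not that it is expected to be large.

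**What to change.** - Delete men's criterion (b) from Table 3.4.2 and reword the first sentence of section 3.4.2 to cover all men enrolled in the trial and their current female partners, in line with section 3.2. Leave the remaining eligibility criteria unchanged. Women's criterion (a) then needs no edit.
- Trace men who have no phone number from an earlier round through the facilitator, local-authority and home-visit routes already in sections 5.1 and 5.2.
- Report, by arm, how many randomised men had never been surveyed before this round and how many of them were reached.

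The cost is one table line, one sentence and a few more tracing attempts. These men will have no earlier-round data, so any analysis that uses baseline values needs a rule for missing ones; that need already exists for men who missed baseline but answered later. If the count proves to be zero, the change costs nothing.

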5.6 Data collection

All interviews and child assessments will be conducted at central venues, such as sector or cell offices, churches, or schools when not in session. The Laterite field team will search for interview

locations where we can assure the privacy of all respondents. Interviews with men, interviews with women, and child assessments will be conducted on different days.

Interviews with adults will be conducted by sex-matched enumerators. Child assessments and collection of anthropometric data will be conducted in the presence of a parent by female enumerators. For the child assessment team, Laterite will prioritize recruiting enumerators with caregiving experience and experience in conducting child assessments.

We anticipate that interviews with adults will take 120 minutes and assessments with children will take 30 minutes (40 minutes if anthropometric data (i.e., height and weight) are collected). Attention will be paid to schedule child assessment appointments when children are not in school, either during weekends or breaks or outside of their school shift.

All interviews will be conducted face-to-face. All data will be collected electronically to ensure quality and data security since paper-based collection has high risks of loss of confidential information. Data collection will be done using android tablets and the surveys will be encrypted and stored on a safe encrypted server location.

Laterite will assign field supervisors to oversee the implementation of fieldwork protocols and adherence to research ethics. The role of the field supervisor is to observe that field procedures are being properly followed, provide individualized feedback to enumerators, attend to adverse events and risks of harm, and conduct backchecks as needed.

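### Living away from the sites and being unable to travel six years after randomisation is treated as ineligibility instead of loss to follow-up, and it also excludes women who still live in the study districts

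*Protocol*

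**What the plan says.** The protocol defines who is to be followed up in several places.

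- Section 3.2 (Study design) says the study will "seek to conduct in-person surveys with all couples enrolled in the original study (who are alive and traceable"). It sets no residence limit.
- Section 3.4.1 (Sampling frame) narrows this to participants "who are living, traceable, and remain eligible for the study".
- Table 3.4.2 lists, as exclusion (a) for men and (b) for women, a person who "Resides outside of the sites selected for this study and specified follow-up locations, and is unable to travel" to a data collection site. The matching inclusion criterion asks for residence in the four districts, "or is able to travel to one of these data collection sites".
- Table 3.4.2, women's inclusion (a), requires the current partner to be a man who is himself eligible for this round. The text above the table adds that her inclusion does not depend on whether he is actually surveyed.
- Section 3.4.4 (Sample selection) says the 1,193 men known to be alive at 21 months will be assessed for eligibility and included in the sample, with their current partners.
- Section 5.2 gives the order of work: confirm eligibility, then invite those who are eligible.
- Section 3.3 says data will also be collected from people who have moved but will travel to a site. Section 5.7 pays 3000 RWF per interview for transport.
- Section 5.6: "All interviews will be conducted face-to-face", at central venues.

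**The concern.** This round is a follow-up of couples who have already been randomised. Eligibility was settled in 2015, and what happens to a couple afterwards belongs to follow-up. Relocation may be linked to work or to the state of the relationship, and the intervention may affect it. If it serves as an entry criterion, two things follow.

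First, a person who has been found and is alive but cannot attend is recorded as never having been due for interview. Attrition can then look smaller than it is, and unevenness between the arms can go unseen. Section 3.4.3 itself expects more attrition than in previous rounds.

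Second, through women's inclusion (a) the rule reaches people who have not moved. A woman in a study district who could walk to the venue is turned away because her partner lives elsewhere and cannot come back. Partner violence is a primary outcome in Table 4.1, and section 5.8.3 has it asked of women only, so her interview is the only source for it.

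**Working it through.** **Step 1. The sections side by side.** Take people who have been traced, are alive and are in a current partnership.

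| Case | Section 3.2 | Section 3.4.4 | Table 3.4.2 | Interview possible in person? |
|---|---|---|---|---|
| A. Man lives away, can travel | sought | in sample | eligible | yes |
| B. Man lives away, cannot travel | sought | in sample, after an eligibility check | excluded, men (a) | no |
| C. Woman lives in a study district, partner is B | sought with the couple | in sample as current partner | ineligible, women's inclusion (a) | **yes** |
| D. Woman lives in a study district, partner eligible but not interviewed | sought | in sample | eligible | yes |
| E. Woman lives away, cannot travel | sought | in sample | excluded, women (b) | no |

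B and E are missing outcomes that the table labels ineligible. C is a loss that the rule itself creates. The sentence protecting women whose partner is not surveyed covers D, where the man is eligible, but not C, where he is not.

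**Step 2. The plan's own counts.** Section 3.2: 575 + 624 = 1,199 couples. Section 3.4.4: 1,193 / 1,199 = 99.5% of the men. Section 3.4.1 prints 576 and 624, which sum to 1,200, so the base used for reporting should be 575 and 624.

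**Step 3. How far the choice of base can move the follow-up figure.** Let *m* be the share of randomised couples excluded because they live away and cannot travel, and *r* the share of the remainder who are interviewed. Follow-up of those eligible is *r*. Follow-up of those randomised is *r* × (1 − *m*). The protocol gives neither value. I assume *r* = 0.94, the 21-month figure for men in section 3.4.3, and a range for *m*. Deaths and ended partnerships are ignored here.

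| *m* (assumed) | Of eligible | Of randomised | Couples out of 1,199 |
|---|---|---|---|
| 5% | 94% | 0.94 × 0.95 = 89.3% | 1,071 |
| 10% | 94% | 0.94 × 0.90 = 84.6% | 1,014 |
| 15% | 94% | 0.94 × 0.85 = 79.9% | 958 |
| 20% | 94% | 0.94 × 0.80 = 75.2% | 902 |

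The same fieldwork can thus be reported as 94% or as anything from 89.3% down to 75.2%, depending only on the base.

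**Step 4. Whether a bias can be sized.** With true outcome rate *p* in an arm and rate *q* among those excluded, the rate observed in that arm is (*p* − *m q*)/(1 − *m*). If *m* and *q* are the same in both arms, nothing is distorted under no effect. For example, *p* = 0.40, *m* = 0.10 and *q* = 0.60 (all assumed) give (0.40 − 0.06)/0.90 = 0.378 in each arm, an odds ratio of 1.00. A distortion needs exclusion to be related to arm and to outcome. The protocol gives neither relation.

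**The case against.** - **The protocol nowhere defines the base of a response rate.** This is true, and section 3.4.4, which puts 1,193 men in the sample, can be read as keeping everyone in the count. A reader might infer that excluded people are certain to leave the denominator. The documents support only that they may: sections 3.4.1 and 5.2 point one way and section 3.4.4 the other. The eligibility rule itself is printed in Table 3.4.2, so it is not a detail left to an analysis plan.
- **Relabelling recovers no data from cases B and E.** This stands. Counting them as lost makes the loss visible and does not remove any bias it causes. Case C is different, because there the change does recover interviews.
- **Most movers may be kept.** Sections 3.3 and 5.7 retain those who can travel and pay for it, so a relocation rate overstates the loss. Only those who have moved and cannot travel are affected, together with partners in case C.
- **Separated men leave through inclusion (c), current partnership.** This stands, so losses from separation should not be charged to the residence rule.
- **Telephone interviews would be the real remedy.** A reader might infer this because in 2020 "a phone survey focused on COVID-19 was conducted with a subsample of 500 men and 498 women enrolled in the study". That was 500/1,199 = 41.7% of men and 498/1,199 = 41.5% of women, on COVID-19 only, and nothing shows that people who had moved away were among those reached. Section 5.6 foresees about 120 minutes per adult interview, section 5.3 allows for couples sharing one telephone, and section 5.8.3 keeps the violence questions from men. Face-to-face interviewing is a defensible choice.
- **The table contradicts itself, using districts in one criterion and sites in the other.** A reader might infer this from section 3.3: "The study site includes communities in 16 sectors within the 4 districts". But the inclusion criterion names the four districts and then calls them data collection sites, so the table can be read consistently. This is a minor wording point.

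**Conclusion.** The point holds as a fault in the eligibility rule and in the accounting of attrition, and it should be corrected. Table 3.4.2 turns a post-randomisation event into ineligibility, against the stated aim of section 3.2 and the sample described in section 3.4.4. Through the partner-eligibility condition it also excludes women who could be interviewed in person. These conclusions rest on the text alone.

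The size is unknown. The gap of 4.7 to 18.8 percentage points between the two follow-up figures (94 − 89.3 and 94 − 75.2) depends on the assumed 5% to 20% exclusion and the assumed 94% response. It illustrates a reporting range and is not a forecast. The number of women in case C cannot be estimated from the protocol. A reader might go on to infer a biased treatment effect of some stated size. The documents do not support one, since they give no relocation rate, no difference between arms and no outcome rate among those who moved.

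**What to change.** 1. Remove residence and ability to travel from the inclusion and exclusion criteria for men and women in Table 3.4.2. Attendance then becomes a matter of follow-up.
2. Reword women's inclusion (a) so that a woman who can attend is interviewed wherever her partner lives. The step in section 5.8.3 of obtaining the man's consent to contact his partner can stay as it is, since section 5.1 begins tracing men by telephone.
3. Count traced people who are not interviewed as lost to follow-up, by arm, with all randomised couples (575 and 624) as the base. Show deaths and ended partnerships on separate lines.
4. Reconcile sections 3.2, 3.4.1, 3.4.2 and 3.4.4 to one statement of who is sought and who is counted, and correct the 576 in section 3.4.1. At the same time use one term for the area (districts or sites) and one for travel, since section 3.3 speaks of willingness and Table 3.4.2 of ability.

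The cost is protocol wording, submitted for ethics review as an amendment, a few additional in-person interviews with women in case C, and one more set of rows in the participant flow. A telephone interview for people who cannot travel is optional and not part of the required change.
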